9.3.4 Additional parameters

Start and stop dates

- **IUD insertion date** is the date on which IUD insertion is documented. This is the starting date (index date) for person-time at risk.
- **Beginning date of study period:** the first date EHR data are available from the data source for this study (as listed within Table 3)
- **End date of study period:** the last date on which EHR data are available from the data source for this study (as listed within Table 3)

- **Date of start of enrollment** (KPNC, KPSC, and KPWA only) is the earliest date of enrollment in the database for the woman (will be used to calculate look-back period)
- **Date of first clinical encounter** (RI only) is the earliest in-person visit in the database for the woman (will be used to calculate look-back period)
- **Date of disenrollment** (KPNC, KPSC, and KPWA only) is the date, after the index date, on which the woman is no longer enrolled in an eligible insurance plan (one gap of ≤ 31 days per year will be allowed)
- **Date of last clinical encounter** (RI only) is the last date on which a woman has an in-person encounter that is recorded in the database
- **Censoring date** is the earliest of the following dates: date of removal of IUD, date of IUD reinsertion, date of start of new pregnancy, hysterectomy date, date of bilateral oophorectomy and other types of sterilization, expiration of IUD (5 years after insertion of Mirena, Kyleena, or unknown IUD, 10 years after insertion for ParaGard and other copper IUDs, 3 years after insertion of Skyla and Liletta), death date, date of disenrollment from the database, or date of last clinical encounter in database.

Other parameters

- **Database:** categorical variable of the four data sources included in the study
- **Continuous enrollment**, in days, that each individual is in the data source will be calculated starting on the earliest date of date of enrollment in database or date of first clinical encounter in database and ending on the earliest of date of disenrollment from database, date of last clinical encounter in database, or end date of study period, allowing up to one 31-day gap in enrollment each year to be considered continuously enrolled. The individual's start and end dates in the enrollment files will be used for KPNC, KPSC, and KPWA. For RI, the start date will be designated as the patient's first clinical encounter within the dataset, and the end date will be the patient's last observation within the dataset. There may be multiple continuous enrollment periods for a woman who moves out of then back into the database.
- **Live birth at most recent delivery:** indicator variable (0 = No, 1 = Yes) for whether the patient had pregnancy ending in live birth within the past 52 weeks.

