9.1 Study design

A retrospective cohort study design will be used to evaluate uterine perforation and IUD expulsion among women with an IUD insertion identified within EHR data. The study will consider the impact of breastfeeding status at the time of IUD insertion and timing of IUD insertion during the postpartum period on the outcomes of perforation and expulsion.

This study will include all women with evidence of an IUD insertion that had at least 12 months of enrollment history preceding IUD insertion. (RI, which does not have enrollment dates, will require a clinical visit at least 12 months before IUD insertion.) The 12-month enrollment before inclusion of IUD insertions will be used to gather baseline data, including data on the exposures, time postpartum, and breastfeeding.

Baseline data—such as patient demographics, patient characteristics (e.g., personal history of gynecologic conditions such as endometriosis), procedure characteristics, medications, and comorbid conditions (e.g., diabetes)—will be collected from all time in the database before the index date (which will be defined as the day of IUD insertion).

Patients will be followed from the time of IUD insertion until the first occurrence of any of the following: uterine perforation, IUD expulsion, IUD removal, indication of IUD reinsertion, indication of new pregnancy, hysterectomy, death, expiration of IUD (e.g., 5 years for Mirena), disenrollment from the database, or end of the study period. All person-time at risk that meets these criteria will be included, and there will be no requirement for minimum or maximum follow-up time. All IUD insertions occurring with at least 12 months of enrollment before the insertion that are noted within the data sources will be included in the study. The index date will be captured for each insertion, and baseline data will be collected for each index date. The main analyses for the study will assess only the first observed IUD insertion for each woman in the database. Secondary analyses will be conducted assessing all subsequent IUD insertions (i.e., after the first observed IUD insertion), as recorded in the database. The sequential number of each insertion as captured in the data for each woman will be collected and included as a baseline covariate within these secondary analyses.

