9.3.3 Outcome measures

- **Person-time at risk** will be calculated from the IUD insertion date until the first occurrence of any of the following: uterine perforation, IUD expulsion, or censoring date.
- **Date uterine perforation confirmed** is the date on which uterine perforation is documented. This may be complete perforation, with IUD migration into the pelvis or abdominal cavity, or partial perforation (i.e., incomplete, with IUD embedded in the myometrium). Cases of both partial and complete perforation will be considered under the umbrella term “perforation.” Cases will be classified as yes, no, or undetermined perforation.
- **Date IUD expulsion confirmed** is the date on which IUD expulsion is documented. IUD expulsion, which is the unintended, spontaneous expulsion of the IUD, will be determined from the EHR, including clinical notes, using algorithms developed during the validation study. Both partial and complete expulsions will be considered under the umbrella term “expulsion.” Cases will be classified as yes, no, or undetermined expulsion.

If both perforation and expulsion (e.g., complete or partial perforation of the *vagina or cervix* by the IUD) occurred and were documented on the same date, then the outcome will be classified as both perforation and IUD expulsion, since these outcomes are evaluated separately throughout this study. If both perforation and IUD expulsion occurred for the same IUD insertion but on different dates, then the earlier date will constitute a stopping date for assessment of all objectives. No analysis will be conducted to assess both perforation and IUD expulsion as a composite outcome or as a subgroup analysis among those with both outcomes.

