There is potential for underreporting of outcomes within the data sources since women will need to seek treatment in order to have an outcome diagnosed. Asymptomatic perforation or IUD expulsion may not be captured. In addition, there may be a lag time between occurrence of perforation or IUD expulsion and the time that the woman seeks treatment. So there is the possibility of missing outcome occurrence. However, this approach is representative of the way that these outcomes would appear within clinical practice, is similar to EURAS-IUD, and there is no reason to believe that this would be differential by exposure group (e.g., breastfeeding vs. not breastfeeding at the time of IUD insertion). So the absolute incidence rates may not be entirely accurate because of potential underestimation due to underreporting or inaccurate coding; or potential overestimation if the algorithm identifies outcomes (e.g., uterine perforation) that are not true cases. However, the ratios should provide an unbiased estimate of any differential risk between exposure groups. We will also assess rates of uterine perforation and IUD expulsion in the literature to provide an external context for the incidence rates.

There is potential for misclassification and missingness of breastfeeding status at the time of IUD insertion. Data sources obtain information for this variable in different ways, with some utilizing linkage to well-child visits for the infant and others using data from the woman's chart either for postpartum visits or on the date of IUD insertion. The complexity of identifying the information within the charts is somewhat mitigated through the involvement of both clinicians and seasoned data informaticists working within each health care system who have experience with identifying such information. Further, the classification of breastfeeding as yes or no is a crude dichotomy and does not follow the potential biological mechanism for breastfeeding to affect uterine perforation or IUD expulsion. For example, breastfeeding once per day differs from eight times per day (the recommendation from one research partner), and thus combining all breastfeeding into one category combines a heterogeneous experience.

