3.7 Start and Stop Dates¹

- *IUD insertion date* is the date on which IUD insertion is documented
- *Beginning date of study period*: the first date EHR data are available from the data source for this study (KPNC, KPSC, and KPWA) or the date when Mirena was launched (RI)
- *End date of study period*: the last date on which EHR data are available from the data source for this study
- *Date of start of enrollment* (KPNC, KPSC, and KPWA only) is the earliest date of enrollment in the database for the woman (will be used to calculate look-back period)
- *Date of first clinical encounter* (RI only) is the earliest in-person visit in the database for the woman (will be used to calculate look-back period)
- *Date of disenrollment from the database* (KPNC, KPSC, and KPWA only) is the date, after the index date, on which the woman was no longer enrolled in an eligible insurance plan (one gap of ≤ 31 days per year will be allowed)
- *Date of last clinical encounter in database* (RI only) is the last date on which a woman had an in-person encounter that was recorded in the database

¹ Note that the actual dates will remain at each data source research partner. The dates may be offset for each patient as an additional data protection measure before transfer of data to RTI-HS.

- *Censoring date* is the earliest of the following dates: date of removal of IUD, date of a subsequent IUD reinsertion, date of start of new pregnancy, hysterectomy date, date of bilateral oophorectomy or other type of sterilization, expiration of IUD, death date, date of disenrollment from database (KPNC, KPSC, and KPWA only) or last clinical encounter (RI only), and end date of study period

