Concomitant gynecological procedure	Indicator variable: 1 = Yes if any of the following procedures occurred on the index date: abortion, aspiration and curettage, dilation and curettage, excision/biopsy of cervix or uterus, ablation, colposcopy and other cervical procedures, hysteroscopy, laminaria, laparoscopy, lysis adhesions, myomectomy, nerve procedure, salpingectomy/oophorectomy 0 = No if none of the above procedures occurred on the index date
Exposures	
Postpartum number of days	Number of person-days, starting on the most recent pregnancy delivery date prior to or on the index date and ending on the index date . There will be a derived postpartum number of days associated with each insertion for each woman. This variable will range from 0 to 365 days and will be missing if the most recent pregnancy delivery date is not recorded or is more than 365 days before the index date .
Postpartum—14-week, dichotomous	Indicator variable: * If postpartum number of days ≤ 98, then postpartum—14-week, dichotomous = 1 * If postpartum number of days > 98 or missing, then postpartum—14-week, dichotomous = 0

Variable	Definition ^a
Postpartum—36-week, dichotomous	Indicator variable: * If postpartum number of days ≤ 252 , then postpartum—36-week, dichotomous = 1 * If postpartum number of days > 252 or missing, then postpartum—36-week, dichotomous = 0
Postpartum—categorical	Categorical variable: * If postpartum number of days ≤ 42 , then postpartum—categorical = 1 (6 weeks or less) * If postpartum number of days > 42 and ≤ 98 , then postpartum—categorical = 2 (> 6 to ≤ 14 weeks) * If postpartum number of days > 98 and ≤ 365 , then postpartum—categorical = 3 (> 14 to ≤ 52 weeks) * If postpartum number of days > 365 or missing, then postpartum—categorical = 0 (> 52 weeks or no delivery)
Outcomes	
Person-time at risk (days, i.e., time to event/censor)	Number of person-days, starting on the index date of IUD insertion and ending on the earliest of date uterine perforation confirmed , date IUD expulsion confirmed , or censoring date . A derived number for person-time at risk will be associated with each IUD insertion for each woman.
Uterine perforation event indicator	Indicator variable: 0 = No date of uterine perforation confirmed during the person-time at risk 1 = Yes, date of uterine perforation confirmed during the person-time at risk

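### Censoring at the start of a new pregnancy codes outcomes found because of that pregnancy as non-events; the stop date is worded two ways and no same-day rule is given

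*Protocol*

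**What the plan says.** **Event date.** For perforation, the outcome date "is the date on which uterine perforation is documented" (Protocol 9.3.3). Expulsion is defined the same way, and SAP 3.2 agrees. Neither document dates an event back to when it occurred.

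**Person-time and event indicator.** SAP Table 1 (section 4.6) counts days from the index date "of IUD insertion and ending on the earliest of" the two outcome dates and the censoring date. Its event indicators equal 1 only when the documented date lies within that person-time.

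**Pregnancy stop, by start date.** Protocol 9.3.4 lists "date of removal of IUD, date of IUD reinsertion, date of start of new pregnancy, hysterectomy date" among the censoring dates. SAP 3.7 has "date of a subsequent IUD reinsertion, date of start of new pregnancy, hysterectomy date".

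**Pregnancy stop, by indication.** Protocol 9.1 ends follow-up at "indication of new pregnancy, hysterectomy, death, expiration of IUD (e.g., 5 years for Mirena") and other stops. Protocol 4.6 and SAP 3 also use an indication of pregnancy rather than its start.

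**Expiry stop.** Protocol 9.3.4 adds "expiration of IUD (5 years after insertion of Mirena, Kyleena, or unknown IUD, 10 years after insertion for ParaGard and other copper IUDs", and 3 years for Skyla and Liletta.

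**Acknowledged limitation.** Protocol 9.9 says that "there may be a lag time between occurrence of perforation or IUD expulsion and the time that the woman seeks treatment". It accepts that absolute rates may be underestimated and expects no difference by exposure group. It does not mention the pregnancy stop.

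**Sensitivity analysis.** The only one described in the methods for the primary objectives (Protocol 9.7.3.1, SAP 6.2.1) replaces weighting with covariate adjustment. None concerns censoring.

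**The concern.** A device that has been expelled unnoticed, or has perforated, may no longer prevent pregnancy. In such a woman the failure leads to the pregnancy, the pregnancy sets the censoring date, and the failure is recorded only when the pregnancy is worked up. She leaves the risk set shortly before her event would have been recorded, because of that event. The Kaplan-Meier and Cox methods in SAP 4.1.3, 4.1.4 and 4.1.6 rely on censoring being independent of the outcome, and here it is not.

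Incidence is at stake first. It is a deliverable in its own right: the regulatory requirement asks for incidence as well as risk factors, and objectives 3-12 report rates and cumulative incidence. The hazard ratios for objectives 1, 2, 20 and 23 are at stake only if the share of events lost differs by breastfeeding status or time since delivery.

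The two wordings add a practical problem. Two programmers following different sections could code the same woman differently.

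**Working it through.** **1. What the definitions imply.** Let t_p be the start of the pregnancy, t_r the day it is first indicated in the record, and t_d the day the outcome is documented. A pregnancy is recognised after it starts, so t_p < t_r. An outcome found because of the pregnancy has t_d ≥ t_r.

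| Stop rule | Outcome documented on day t_r | Outcome documented after t_r |
|---|---|---|
| Start of pregnancy (Protocol 9.3.4, SAP 3.7) | t_d > t_p: coded 0 | coded 0 |
| Indication of pregnancy (Protocol 4.6 and 9.1, SAP 3) | tie with censoring: undefined | coded 0 |

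The plan says what to do when perforation and expulsion share a date (Protocol 9.3.3, SAP 3.2). It gives no rule for an outcome that shares a date with a censoring event. The gap also affects an outcome documented on the day of device removal.

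**2. The plan's own power figure.** Inputs are in Protocol 9.5 and Table 4: 60,000 insertions, risk 1.3 per 1,000, allocation 60:40, hazard ratio 2.0, two-sided 0.05.

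- Events: 60,000 × 0.0013 = 78.
- Power = Φ(√(78 × 0.6 × 0.4) × ln 2 − 1.96) = Φ(1.04) = 85.1%. Stated: 85%.
- For the 5:70 comparisons: 168,750 × 0.0013 = 219.4 events, exposed share 1/15, power 72.6%. Stated: 73%.

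Table 4 therefore reproduces. That confirms the inputs; it is not evidence for this point.

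**3. Equal loss in both groups.** The share lost is not in the documents. The range below is assumed, and 1.3 per 1,000 is taken as the risk with no loss. Risk becomes 1.3 × (1 − f), and events scale the same way.

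| Share lost, f | Risk per 1,000 | Events, objective 1 | Power, objective 1 | Power, 5:70 |
|---|---|---|---|---|
| 0 | 1.30 | 78.0 | 85.1% | 72.6% |
| 5% | 1.24 | 74.1 | 83.2% | 70.4% |
| 10% | 1.17 | 70.2 | 81.2% | 68.1% |
| 20% | 1.04 | 62.4 | 76.5% | 63.0% |
| 30% | 0.91 | 54.6 | 70.9% | 57.2% |

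The hazard ratio stays at 2.00 in every row. The power calculation uses a 1-year risk, so only the pregnancy stop could affect it; the earliest expiry is at 3 years.

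**4. Unequal loss.** For rare events, observed HR ≈ 2.0 × (1 − f1)/(1 − f0), with f1 the share lost in the exposed and f0 in the unexposed.

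- 5% vs 10%: 2.0 × 0.95/0.90 = 2.11
- 10% vs 5%: 2.0 × 0.90/0.95 = 1.89
- 2% vs 10%: 2.0 × 0.98/0.90 = 2.18

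**5. Comparison with sampling error.** For objective 1 the standard error of the log hazard ratio is about 1/√(78 × 0.6 × 0.4) = 0.231. A hazard ratio of 2.0 would have an interval of about 2.0 × exp(±1.96 × 0.231), or 1.27 to 3.15. The largest shift in step 4 is ln(2.18/2.00) = 0.086, about 0.37 of a standard error.

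**The case against.** **The loss is already disclosed.** Protocol 9.9 admits lag and missed outcomes, says absolute rates may be too low, notes that ascertainment reflects practice and resembles the earlier European cohort, and expects no difference by exposure. This stands as general disclosure. It does not say that one censoring rule removes a particular class of outcome, and no planned output checks the expectation.

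**The events are not necessarily all lost.** A reader might infer that pregnancy-detected outcomes can never be counted. That follows only from the start-of-pregnancy wording. Under the other wording an outcome documented on the day of the indication might count, so the documents do not settle it. Outcomes found later in the work-up are lost under both.

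**Expiry is a different matter.** A reader might extend the argument to outcomes found at a removal after expiry and conclude that the primary hazard ratios are biased by that stop too. The documents do not support this. Expiry is a defensible end to the at-risk window, and it is set by product, not by breastfeeding or time since delivery. For 5-year and unknown devices, later-documented outcomes also lie outside the 1- and 5-year horizons for cumulative incidence and rate ratios (SAP 6.2.2.1, Protocol 9.7.3.4.2). Outcomes that occurred before expiry but were found afterwards do go uncounted, which justifies a count and no more.

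**The size is assumed.** This is correct. The shifts in step 4 need two- to fivefold differences in loss between groups, no section supports such differences, and their direction is unknown.

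**The remedy takes more than one extra date.** Sites must identify the pregnancy-related finding from codes and notes and attribute it to the index device, with an attribution window that is a convention. This stands and is reflected in the cost below.

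**Conclusion.** The point holds for the pregnancy stop. By the plan's own definitions, a perforation or unnoticed expulsion found because of a pregnancy is coded as a non-event under Protocol 9.3.4 and SAP 3.7. This understates incidence and cumulative incidence for both outcomes to an unknown degree. Hazard ratios are affected only if the loss differs between exposure groups. That is possible, but the documents neither show it nor plan to test it.

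The values 1.89 to 2.18 illustrate assumed losses and should not be read as estimates of bias in this study. Even the largest is small beside the sampling error expected for objective 1. The case for acting is that the mechanism is built into the definitions, its size can be counted from records the sites hold, and the stop-date wording has to be reconciled in any case.

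**What to change.** 1. **Reconcile the stop date.** Use one definition of the pregnancy stop in Protocol 4.6, 9.1 and 9.3.4 and SAP 3 and 3.7. State that an outcome documented on the same day as a censoring event counts as an event.

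2. **Add a pre-specified sensitivity analysis.** Keep the primary person-time rule. For objectives 1, 2, 20 and 23, and for the matching incidence estimates, also count as an event at the censoring date any perforation or expulsion of the index device first documented after the pregnancy start and within a stated window. Fix the window before the outcome data are examined. Report the number of such events by exposure group, since this tests directly whether the loss is differential. Some of these outcomes may have occurred after conception, so present the result alongside the primary analysis, not as a replacement.

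3. **Expiry.** At most, report how many outcomes of the index device were first documented after expiry. No change to the primary analysis is needed.

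**Cost.** One post-censoring outcome date in each site extract, the site work to attribute it to the index device, one table, and an attribution window that is a convention. Any expiry count has to be flagged at the sites, because brand is not sent to the coordinating centre (Protocol 9.10).

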9.4 Data sources

There will be four EHR data sources for this study: KPNC, KPSC, KPWA, and RI. Data in different files within each data source will be linked by the patient's identification number. Descriptions of each data source follow (Sections 9.4.1 through 9.4.4).

9.4.1 Kaiser Permanente Northern California

The KPNC region in California extends from Santa Rosa and Sacramento in the north, to Modesto in the east, and south to San Jose and Fresno and includes the entire San Francisco Bay Area. It covers 21 hospitals and 238 medical offices. KPNC covers approximately 4 million patients, representing half of the commercially insured patients and one quarter of the Medicare patients in the area.

Data for KPNC are housed within a comprehensive EHR system that captures every patient encounter in every department, including hospital, emergency, ambulatory surgical, specialist, and generalist care encounters; clinic visits and telephone encounters; physiological measures; procedures; laboratory and radiology testing; and diagnoses. The comprehensive EHR system was fully implemented in 2009. Standardized research datasets—including enrollment,

sociodemographics, pharmacy, encounters, diagnoses, procedures, vital signs, census, and laboratory results—are maintained for the purposes of research. Data are linked across all databases via a unique identifier. Infant records are maintained and can be linked to the mother’s delivery record data.

In the validation study, continuous enrollment in KPNC was measured via enrollment files. Of all IUD insertions in this data source, 67% (more than 100,000) were in women with at least 12 months of continuous enrollment before the date of insertion.

